#### Non-Clear Cell Subjects

Tumor tissue, from primary or metastatic site (excluding bone), will be submitted to the Sponsor-designated CLIA certified laboratory for ENPP3 determination by IHC. An IHC H-score of  $\geq 15$  is required for non-clear cell subjects to qualify for study screening. IHC H-scores for ENPP3 eligibility will not expire for the duration of the study (i.e., there is no time limit from prescreen qualification to screening start).

Every effort will be made to report the IHC H-score to the investigator  $\leq 72$  hours of sample receipt at the Sponsor-designated CLIA certified laboratory provided that the specimens were received in good condition along with all required documents fully completed. Refer to Study Guide for details.

#### Clear Cell Subjects

Clear cell histology subjects are not required to be screened for target expression to qualify for the study, however, the source and availability of archive tissue must be confirmed to meet study eligibility criteria (Inclusion #6). Tissue should be submitted for IHC testing  $< 3$  months from main study consent form signature date. Consent to provide tissue is

included in the main study informed consent form. Clear cell histology subjects' specimens will be batch assayed during the study. The IHC H-score will be reported back to the investigator for information only when the data become available.

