**Prescreening**

Subjects with RCC of non-clear cell histology must sign the prescreening ICF and be prescreened for ENPP3 expression prior to undergoing screening procedures for the main study. Tumor tissue, from a primary or metastatic site (excluding bone), will be submitted to the Sponsor-designated CLIA certified laboratory for ENPP3 determination by IHC. An IHC H-score of  $\geq 15$  is required for non-clear cell subjects to qualify for study screening. IHC H-scores for ENPP3 eligibility will not expire for the duration of the study (i.e., there is no time limit from prescreen qualification to screening start). Every effort will be made to report the IHC H-score to the investigator  $\leq 72$  hours of sample receipt at the Sponsor-designated CLIA certified laboratory provided that the specimens were received in good condition along with all required documents fully completed.

Clear cell histology subjects are not required to be screened for target expression to qualify for the study but must provide tissue during the study. Consent to provide tissue is included in the main study informed consent form. Clear cell histology subjects' specimens will be batch assayed during the study. The IHC H-score will be reported back to the investigator for information only when the data become available.

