#### 1.1.3 ENPP3 Antigen Target and Expression in Cancer

The antigen target, ENPP3 (referred to as AGS-16), was cloned from a patient renal carcinoma specimen and identified as an 875 amino acid type II single transmembrane

antigen that is upregulated in the majority of renal and in a subset of hepatocellular cancers. Sequencing of AGS-16 identified it as ENPP3 (CD203c), one of 7 members of a family of cell surface ectonucleotide phosphodiesterases-pyrophosphatases (PDEs), ENPP1-7 (Deissler et al, 1995) (Jin-Hua et al, 1997) (Buhring et al, 2001) (Goding et al, 2003) (Stefan et al, 2005). The physiological substrate of ENPP3 is unknown, but studies have suggested that the enzyme catalyzes extracellular nucleotides (e.g., ATP; Goding et al, 2003).

Immunohistochemical (IHC) and tissue cross reactivity studies have shown restricted expression of ENPP3 in normal tissues predominantly in a subset of cells in the kidney cortex. Low levels of staining were also observed in the epithelium of the fallopian tube, a subset of cells within gastrointestinal tract epithelium, in uterine endometrium, parotid gland, and the cortex of the thymus. Flow cytometric analysis has also shown that ENPP3 is expressed on activated basophils and mast cells (Buhring, 1999). ENPP3 is highly expressed in approximately 90% renal clear cell carcinoma; 69% papillary RCC and 27% hepatocellular carcinoma as determined at Agensys by staining tissue microarrays with an immunohistochemistry antibody specific for ENPP3.

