### **2.2 Study Design and Dose Rationale**

#### **2.2.1 Study Design**

This multi-center, open-label, randomized study will enroll subjects with metastatic RCC of all histologies who have evidence of progression on or after the last regimen received and have also received at least 2 prior systemic regimens 1 of which is an anti-VEGF agent (clear cell subjects).

Non-clear cell RCC is a heterogeneous group of tumors typically not driven by von Hippel-Lindau (VHL) gene and sensitivity to anti-VEGF treatments differ from that shown in clear cell RCC. Hence, subjects with non-clear cell histology are only required to have progressed on or after only at least one anti-VEGF regimen.

Subjects with non-clear cell histology must also have ENPP3 positive immunohistochemical (IHC) staining at prescreening. Positivity is defined as an IHC H-score  $\geq 15$ . Non-clear cell subjects whose tissue has an IHC H-score of  $\geq 15$  will qualify to screen for the study.

Clear cell subjects are not required to be screened for ENPP3 to qualify for the study, but subjects must submit tissue during the study for retrospective target expression assessment by IHC.

Subjects will be randomized at 1:1 ratio to either AGS-16C3F or axitinib. Randomization will be stratified according to Eastern Cooperative Oncology Group (ECOG) Performance

Status (0 or 1), the number of prior systemic RCC regimens (2 or > 2), and RCC histology (clear cell or non-clear cell).

For stratification purpose:

- Non-clear cell subjects who have progressed after only one prior anti-VEGF regimen will be regarded the same as those clear cell subjects who have progressed after 2 prior systemic RCC regimens.
- Non-clear cell subjects who have progressed after > 1 prior systemic RCC regimens will be regarded the same as those clear cell subjects who have progressed after > 2 prior systemic RCC regimens.

AGS-16C3F will be administered at 1.8 mg/kg as a single 60-minute IV infusion once every 3 weeks.

Axitinib is a commercial product and will be administered as defined in its product label. Axitinib will have a starting dose of 5 mg, twice daily continuously, by mouth. Axitinib dose may be adjusted during the study as needed as defined in the product label and local institutional guidelines, in doses ranging from 2 to 10 mg, twice daily continuously, by mouth.

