## **2.3 Endpoints**

### **2.3.1 Primary Endpoints**

To evaluate the PFS of AGS-16C3F compared against axitinib (Investigator radiology assessment per RECIST v.1.1).

PFS is defined as the time from the date of randomization to the earliest of documented disease progression as defined by RECIST v.1.1 or death from any cause.

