## 5.5 Efficacy Assessment

Response and progression will be evaluated in this study using RECIST v.1.1, refer to Appendix [12.6](#). Investigator's radiographic disease assessment will be used for treatment decisions.

Disease assessments will be performed every 8 weeks ( $\pm 7$  days) counting from C1D1. Bone imaging will be performed every 12 weeks ( $\pm 7$  days) counting from C1D1 (only subjects with bone disease at screening).

Those subjects who discontinued the study for reasons other than objective disease progression by RECIST v.1.1 will continue to have disease assessments every 8 weeks ( $\pm 7$

days) counting from C1D1. This will continue until subject has radiologically confirmed progression, initiates a new therapy, study closure or subject dies.

Scans will be read on site.

CT scan with contrast (chest, abdomen, and pelvis) is the preferred modality for tumor assessment. MRI is acceptable if local standard practice, or CT scans are contraindicated in a subject (e.g., subject is allergic to contrast media). All other RECIST-approved scanning methods such as x-ray are optional. PET-CT scans must use contrast. The modality chosen for the subject must be used throughout the study.

Additional instructions for imaging assessments can be found in the study guide. The assessment will include tumor measurements for target lesions, nontarget lesions, and any new lesions. An overall assessment will be characterized for a given time point evaluation. At the end of study for that subject, the best overall response to the study regimen will be characterized. To ensure comparability, the screening and subsequent assessment of response should be performed using identical techniques. The same individual should assess images for any 1 subject for the duration of the study if possible.

For subjects with known treated stable brain metastases at study entry, it is recommended that repeat imaging also include the brain and the same methods used to detect brain lesions at baseline are to be used to follow the lesions throughout the study.

Per RECIST v1.1, lesions that cannot be accurately measured such as bone lesions and previously radiated lesions should not be selected as measurable lesions.

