#### **5.5.2 Evaluation of Nontarget Lesions**

To achieve unequivocal progression on the basis of nontarget lesions, there must be an overall level of substantial worsening in nontarget disease such that, even in presence of SD or PR of target lesions, the overall tumor burden has increased sufficiently to merit discontinuation of therapy. A modest increase in the size of 1 or more nontarget lesions is usually not sufficient to qualify for unequivocal progression.

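### Clear-cell subjects' ENPP3 H-scores are returned to open-label investigators during the trial with no stated use, an avoidable risk to investigator-assessed PFS

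*Protocol*

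**What the plan says.** Protocol Section 5.2.1 (Clear Cell Subjects) and the Synopsis (Prescreening) say: "Clear cell histology subjects' specimens will be batch assayed during the study". Both continue: "The IHC H-score will be reported back to the investigator for information only when the data become available". Neither delays release until progression, data cut-off or database lock, and neither limits it to one arm.

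Other parts of the plan bear on this:

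- **Use of the score.** An H-score of at least 15 is an entry criterion for non-clear cell subjects only (Protocol Section 3.2, criterion 2a). Clear-cell subjects "must submit tissue during the study for retrospective target expression assessment by IHC" (Protocol Section 2.2.1). No treatment rule refers to the score. It is not among the subgroup factors named in Protocol Section 7.4.1.3 or SAP Sections 7.6.2 and 17.1.5.
- **Who receives it.** The trial is open label (Protocol Section 2.2.1) and the primary endpoint is PFS on the investigator's reading (Section 2.3.1). Section 5.5 adds: "Investigator's radiographic disease assessment will be used for treatment decisions". Section 6.1 lets the investigator stop treatment on judgment.
- **What happens to a switch.** New anticancer therapy before documented progression is censored in the primary analysis (Protocol Section 7.4.1.1 and Table 13; SAP Section 17.1.2.1, Set 1).

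**The concern.** The person who judges the primary endpoint is handed a marker of expected benefit from one of the two drugs, with the arm already known. The protocol supplies a benchmark for reading it: a non-clear cell subject scoring below 15 could not have been screened. An investigator who learns that a clear-cell subject on AGS-16C3F scored low has a reason to doubt the drug.

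There are two routes from that doubt to the result:

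- **Progression calls.** Non-target progression calls for judgment. Substantial worsening is required, and the test is whether "the overall tumor burden has increased sufficiently to merit discontinuation of therapy". An equivocal scan can be read either way.
- **Switching.** A discretionary stop followed by new therapy removes the subject from the primary analysis by censoring. If the switch was prompted by the score, that censoring is informative.

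A high score could act in the opposite direction, by delaying a progression call or encouraging continued treatment.

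**Working it through.** **1. The plan's own figure.** Inputs from Protocol Section 7.1: HR = 4/6 = 0.667, one-sided alpha 0.10, 80% power, 1:1 allocation.

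- Events (Schoenfeld) = 4 × (1.2816 + 0.8416)² / (ln 0.667)² = 110, as stated.
- Power at 110 events = Φ(−ln(0.667) × √110/2 − 1.2816) = 80.1%.
- Critical observed HR = exp(−2 × 1.2816/√110) = 0.783, as stated.

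**2. How many subjects are affected.** Protocol Section 2.2.3 caps non-clear cell subjects at 26 of 134. Clear cell is then at least 134 − 26 = 108, or 108/134 = 80.6%, about 54 per arm.

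**3. Whether scores can arrive before the PFS event.** Section 5.2.1 asks for tissue within 3 months of consent, while the tumour tissue footnote to Table 1 allows it at any point during the study. Batch dates are not given. Under exponential PFS with the planned medians, the share still event-free is:

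| Time | AGS-16C3F (median 6) | Axitinib (median 4) |
|---|---|---|
| 3 months | 2^(−3/6) = 71% | 2^(−3/4) = 59% |
| 6 months | 2^(−6/6) = 50% | 2^(−6/4) = 35% |

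At 3 months, 29% and 41% would already have had an event. Release around then would reach most subjects before their event; later batches would reach fewer.

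**4. Sensitivity of the test to bias.** The documents give no size for any bias. Let b be an assumed factor multiplying the observed HR, so that P(reject) = Φ(−ln(HR × b) × √110/2 − 1.2816).

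| Assumed b | Type I error (true HR 1) | Power (true HR 0.667) |
|---|---|---|
| 0.90 | 23.3% | 91.9% |
| 0.95 | 15.6% | 86.7% |
| 1.00 | 10.0% | 80.1% |
| 1.05 | 6.2% | 72.2% |
| 1.10 | 3.7% | 63.5% |

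This shows how a given bias would act on the test. It does not show that releasing H-scores produces a bias of that size.

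**5. Existing safeguards.**

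- *Blinded central PFS* (Protocol Section 2.3.2; SAP Section 17.2.3.1) addresses reading bias but not switches, and it is secondary. Current Section 5.5 has scans read on site, and Attachment 1 (Amendment 5) records that central submission has ended.
- *Investigator-versus-central concordance* (SAP Section 17.2.3.7) covers best response, objective response and disease control, not progression dates.
- *Censoring Set 2* (SAP Section 17.1.2.2) counts switches and treatment discontinuations as events. It removes the informative censoring, but a score-driven stop then enters as a failure.
- *Review of censoring times by arm* (SAP Section 17.1.6) could reveal an imbalance but would not link it to the score.

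**The case against.** The strongest reply is that the increment is small. Knowledge of the arm already permits every bias described here. The protocol reports that "ENPP3 is highly expressed in approximately 90% renal clear cell carcinoma" (Section 1.1.3), so most scores would tell an investigator only what was expected. Many may arrive after the PFS event. RECIST asks for substantial worsening and unequivocal progression, which limits discretion. Central PFS, Set 2 and the censoring review exist. All of this stands as a limit on size. None of it gives a reason to release the score.

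A second reply is that subjects may be owed the result. Protocol Section 8.2.3.2 requires prompt disclosure of new information relevant to consent, and the consent form is not available for this review. The point deserves checking, but it is weak for a result the protocol itself labels as information only, and release at documented progression largely meets it.

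A third is lateness. Version 6.0 is dated August 2020, with the study planned to end in 3Q2020, so scores may already be out. That changes the remedy, not the point.

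A reader might also infer a firm loss of power: 10% of 54 gives about 5 of 67 AGS-16C3F subjects with a discouraging score; a 50% to 100% rise in their hazard moves the HR from 0.667 to about 0.69–0.72, and power falls to about 74%–68%. The documents do not support this. The 90% figure is high expression on tissue microarrays, not H-score of at least 15, and no share of clear-cell tumours below 15 is given. The hazard increase is invented and is applied from randomization, before any score exists. An early switch is censored under Set 1, so it does not add an event. Only one direction is counted.

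**Conclusion.** The concern holds as an avoidable risk, not as a demonstrated bias. The text establishes that clear-cell H-scores, for at least 108 of 134 subjects if the cap is respected, reach the open-label assessor of the primary endpoint during the study and serve no stated purpose there. The two routes to bias follow from the protocol's own rules on progression, discontinuation and censoring.

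Direction and size are unknown. The figures for b are illustrative and rest on an assumed multiplicative bias, 110 events and proportional hazards.

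A reader might go further and conclude that only the AGS-16C3F arm is exposed. The documents do not say so: scores are returned in both arms, and nothing shows that decisions on axitinib are unaffected. A mainly one-arm effect is a plausible inference because ENPP3 is the target of AGS-16C3F, and no more than that. Nor is a planned marker analysis being damaged, since none is planned.

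This is a cheap improvement worth making. It does not invalidate the primary analysis.

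**What to change.** In Protocol Section 5.2.1 and the Synopsis, replace the sentence on reporting clear-cell scores with: *Clear-cell subjects' H-scores will not be released to investigators until the subject's documented progression or the data cut-off for the Main Analysis, whichever is earlier.* Non-clear cell prescreening results continue to be reported, because they decide eligibility.

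Where scores have already been released, record the release date for each subject and report PFS calls and censoring by arm before and after release. Split each subject's follow-up at the release date, because only subjects still event-free can have a score released before their event. Treat the comparison as descriptive, and state the limitation in the study report.

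The cost is one sentence and an instruction to the laboratory. The 110 events, the one-sided 0.10 level, the sample size and eligibility are unchanged. Investigators receive an information-only result later, and the consent wording should be checked for any promise to return results.

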### 5.2.2 Prescreening Period

Prescreening of target expression testing is only required for non-clear cell subjects. Refer to details in Section [5.2.1](#). Non-clear cell subjects must sign a prescreening informed consent form to obtain and submit tissue for the study and be prescreened for ENPP3 expression prior to undergoing screening procedures for the main study. Only those with an IHC H-score  $\geq 15$  qualify to proceed with screening. A copy of all signed and dated informed consent forms must be given to the subject before any study specific procedure is performed.

### 5.2.3 Screening Period

All subjects with RCC of clear cell histology and subjects with RCC of non-clear cell histology who have received an IHC H-score of  $\geq 15$  are eligible for screening.

All subjects who are eligible to screen will sign the main study ICF  $\leq 28$  days of C1D1. A copy of all signed and dated informed consent forms must be given to the subject before any study specific procedure is performed. Subjects may undergo study screening procedures prior to giving informed consent provided they are considered standard of care.

The following screening procedures must be performed  $\leq 28$  days of the C1D1 date, unless otherwise noted.

- Medical history, including previous renal cancer therapies; refer to Section [5.3.2](#)
- Physical Examination including vital signs (blood pressure, heart rate, and respiration rate) and weight
- ECOG Performance Status score; refer to Appendix [12.5](#)
- Hematology, chemistry, CRP, and PT/aPTT evaluations ( $\leq 10$  days of the C1D1; refer to Section [5.6.3](#))
- Thyroid Function Tests; refer to Section [5.6.3](#)
- uPCR
- Serum pregnancy test (women of childbearing potential;  $\leq 10$  days of the C1D1)
- Electrocardiogram (ECG) (in triplicate, approximately 3-5 minutes in between ECGs);  $\leq 10$  days of the C1D1; refer to Section [5.6.4](#)
- Disease assessment; refer to Section [5.5](#)
  - CT scan of the chest, abdomen, and pelvis (Magnetic Resonance Imaging (MRI) is acceptable to assess disease extent if used throughout the study).
  - Imaging of the brain (e.g., MRI or CT), if clinically indicated
  - Bone imaging, if clinically indicated. The imaging method will be any imaging modality per local or institutional standard of care (SOC) (e.g., NaF PET, MRI Bone, Tc-99 Bone Scan, etc.)

- Complete eye exam for all subjects; refer to Section 5.6.5
- Complete ESQ for both Cancer Treatment History and Screening sections; refer to Section 5.6.5.1
- Randomization; refer to Section 5.2.5 for additional details
- Tumor Tissue; refer to Section 5.2.1
- Complete and submit an eligibility worksheet for review. Please see the Study Guide for the form and for complete instructions

Subjects who do not meet the eligibility criteria may be re-screened at the discretion of the Investigator.

#### 5.2.4 Enrollment

In this study, subjects are considered enrolled once randomized.

#### 5.2.5 Randomization

See Section 4.4 and the separate relevant study manuals for details. Randomization will occur after screening has been completed and must be done  $\leq 5$  days of C1D1. Randomized subjects will not be replaced, whether or not, the subject receives study treatment.

#### 5.2.6 Treatment Period

On C1D1, all procedures, other than post-infusion specific procedures, must be performed BEFORE first dose of study drug is administered and meet all inclusion and exclusion criteria.

During the treatment period, subjects who have a standard of care tumor biopsy or surgery, will have the opportunity to submit part of the sample for ENPP3 analysis. The subject will indicate their choice in the informed consent form.

##### 5.2.6.1 Cycles 1 – 4

All predose procedures below may be performed  $\leq 4$  days in advance of the actual dosing day, with the exception of the following which must be done on the dosing day:

- Vital signs
- ECG (C1D1 Only)
- Predose PK sample collection for AGS-16C3F subjects on Cycles 2-4. Predose PK sample for Cycles 2-4 must be collected anytime before AGS-16C3F drug administration on the day of infusion.
- Physical exam and body weight
- Vital signs; refer to Section 5.6.1
  - For AGS-16C3F Subjects: On the days of study drug administration, vital signs will be taken predose, and approximately 30 minutes after administration of study drug

- For axitinib Subjects: Vital signs will be taken once at each clinic visit
- ECG (C1D1 only); refer to Section 5.6.4
  - For AGS-16C3F Subjects: It will be done predose (anytime predose on actual dosing day) and 2 hours after the end of infusion, when the total prescribed dose has been administered (e.g., 2 h after the end of infusion), both in triplicate (approximately 3-5 minutes in between ECGs). Ensure that the subject is in the same position for every reading
  - For axitinib Subjects: ECG will be taken in triplicate (approximately 3-5 minutes in between ECGs) predose (anytime predose on actual dosing day). Ensure that the subject is in the same position for every reading
- ECOG Performance Status; refer to Appendix 12.5
- Hematology, chemistry, CRP, and PT/aPTT; refer to Section 5.6.3
- Thyroid Function Test, every odd cycle (e.g., Cycle 1, Cycle 3, etc.); refer to Section 5.6.3
- uPCR, every odd cycle (e.g., Cycle 1, Cycle 3, etc.); refer to Section 5.6.3
- Complete eye exam for AGS-16C3F subjects only will be done after the Cycle 2 Day 1 dose but before the Cycle 3 Day 1 dose, and as clinically indicated; refer to Section 5.6.5
- Complete ESQ at every scheduled and unscheduled visit; refer to Section 5.6.5.1
- PK and ADA blood samples will be collected for AGS-16C3F subjects only; refer to Table 1 and Table 2
- Disease assessment; refer to Section 5.5

